## **2. Objectives (include all primary and secondary objectives)**

Specific Aim 1: To test whether nasal CPAP reduces the incidence of hypoxia during procedural sedation with propofol as compared to usual care. Hypothesis: A randomized clinical trial of an intervention to reduce airway obstruction (nasal CPAP) will decrease the incidence of hypoxic events ( $<90\% \geq 15s$ ) compared to usual care in patients undergoing procedural sedation.

Specific Aim 2: To determine the duration, magnitude and mechanism of hypoventilation and its association with hypoxia in subjects undergoing procedural sedation. Hypothesis: By determining minute ventilation, transcutaneous CO2 and sedation depth while measuring end-tidal CO2, it will be possible to relate ventilation to hypoxic events, sedation depth and airway obstruction. Further, reductions in the incidence of hypoxia in the intervention group will be consistent with the hypothesis that loss of airway motor tone underlies hypoventilation and associated hypoxia.

Specific Aim 3: To characterize the physiologic state when end-tidal capnography is insufficient for detecting hypoventilation. Hypothesis: The amplitude of the capnographic signal is not representative of the adequacy of ventilation due to artifact from loss of airway motor tone during procedural sedation.

Specific Aim 4: To determine if there short chain fatty acid serum concentration is protective for procedural sedation induced hypoventilation, obstruction and hypoxia: Hypothesis: Higher concentration

of short chain fatty acids will be reduce the risk of hypoventilation, obstruction, and hypoxia and suggests a link between respiratory function and gut microbiome.

**3. Background** (briefly describe pre-clinical and clinical data, current experience with procedures, drug or device, and any other relevant information to justify the research)

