#### **4. Study Procedures**

Study design, including the sequence and timing of study procedures (distinguish research procedures from those that are part of routine care).

This study is a randomized controlled trial comparing oxygen delivery with nasal CPAP versus standard care (delivery via nasal cannula or standard facemask) during propofol-based sedation for endoscopic procedures. The primary outcome will be the rate of oxygen desaturation below 90% for  $\geq 15$  seconds. Secondary outcomes are the degree of hypoventilation measured by continuous transcutaneous carbon dioxide (TcCO2), the change in minute ventilation (MV) and obstructive episodes measured by impedance-based respiratory volume monitoring, and depth of anesthesia measured by bispectral index (BIS) monitoring. The adequacy of standard ETCO2 monitoring will also be assessed. In addition, all clinical data utilized in routine practice will be recorded, including drug dosing, method of drug administration, blood pressure changes, frequency of interruption of procedure for airway maneuvers or rescue, length of stay in the recovery area, and any complications that are identified.

Subjects will be recruited from the patient population scheduled for MAC with sedation for gastrointestinal endoscopic procedures at the Johns Hopkins Hospital Endoscopy Center on Zayed 2. Patients scheduled for colonoscopy, EGD (including EGD with biopsy, ultrasound, PEG

placement, or enteroscopy ) or combined upper and lower endoscopic procedures predicted to last longer than 10 minutes and for which MAC with sedation is the planned anesthetic technique will

Page 5 of 12

be considered for the study. A study team member will screen the endoscopy schedule for potential subjects. We will direct our recruitment to patients with documented OSA or a BMI  $\geq 30$ , but we not limit it to just those patients. Written, informed consent will be obtained from interested eligible subjects or their representative.

As part of routine care, all patients undergoing MAC with sedation receive an IV in the preoperative area. During the placement of this IV up to 15 mL of blood will be collected for short chain fatty acids measurements and possibly the measurement of biomarkers and other compounds. The written consent form will include permission from the participant to store their blood for future research.

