All subjects will also have standard, routine monitors placed by the treating team, including blood pressure, ECG, pulse oximetry, and EtCO2. Subjects will be randomized to either 1) receive oxygen by nasal mask (nCPAP) with CPAP of 10 mmHg or 2) standard oxygen therapy. Subjects randomized to nCPAP will have a nasal facemask (SuperNOVA) placed approximately 5 minutes prior to the procedural start. The mask attaches to the anesthesia circuit, oxygen flow will be set at 10 lpm, and the CPAP of 10 will be set by turning the "pop-off" valve to 10 mmHg. Subjects randomized to standard care will have oxygen delivered by nasal cannula or simple facemask with oxygen level set by the treating providers. The CPAP level of 10 will be chosen because previous studies suggest that 95% of airway obstruction can be alleviated with a CPAP of 7.1, and it is convenient marked on the anesthesia "pop-off" valve, ensuring standardization. For the CPAP group, flow below 10 lpm will be allowed in cases in which the patient or provider does not tolerate higher flows. For practicality, providers and patients will not be blinded to the intervention because application of the nasal mask is obvious. While the clinical team will have access to all of the routine monitors, they will be blinded to the research monitor data, which will include TcCO2 monitoring, respiratory volume monitoring (RVM), and BIS. Researchers analyzing the data will be blinded to the intervention.

All subjects will receive a routine propofol-based anesthetic per the treating clinical team. A study team member will record all airway maneuvers or interventions performed by the anesthesia team during the procedure, including changes in oxygen flow, ventilatory assistance, jaw thrust, or placement of an oral or nasal airway. Further, the duration of the endoscopic procedure and any anesthesia related interruptions will be recorded. The study duration will be entirely within the time period of the patients' visit to the endoscopy suite. All study monitors will be removed when the participants are discharged to home or transferred to the ward depending on the clinical routine or needs.

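### Does Aim 2 need rewording because a fall in hypoxia could reflect better oxygen delivery rather than relief of airway obstruction?

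*Combined protocol and SAP*

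**What the plan says.** Specific Aim 2 seeks the duration, magnitude and mechanism of hypoventilation and its link with hypoxia. Its hypothesis has two parts. The first uses minute ventilation, transcutaneous CO2, sedation depth and end-tidal CO2 to relate ventilation to hypoxic events and airway obstruction. The second, added as a further remark, is that "reductions in the incidence of hypoxia in the intervention group will be consistent with the hypothesis that loss of airway motor tone underlies hypoventilation".

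Section 4 sets out oxygen delivery by arm:

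- **CPAP arm:** "Subjects randomized to nCPAP will have a nasal facemask (SuperNOVA) placed approximately 5 minutes prior to the procedural start". On that circuit "oxygen flow will be set at 10 lpm", although "flow below 10 lpm will be allowed in cases in which the patient or provider does not tolerate higher flows".
- **Control arm:** "Subjects randomized to standard care will have oxygen delivered by nasal cannula or simple facemask with oxygen level set by the treating providers". No flow or start time is given.
- **Blinding:** "providers and patients will not be blinded to the intervention because application of the nasal mask is obvious". The clinical team does not see the transcutaneous CO2, respiratory volume or BIS data, and those analysing the data are blinded to arm.
- **Records:** a study team member logs airway manoeuvres and interventions, "including changes in oxygen flow, ventilatory assistance, jaw thrust, or placement of an oral or nasal airway". More generally, "all clinical data utilized in routine practice will be recorded".

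Sections 4 and 7 list obstructive events, minute ventilation and transcutaneous CO2 among the secondary outcomes. Section 3 states the between-arm expectation that CPAP will reduce obstruction and that hypoventilation will be lower in the intervention arm.

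**The concern.** A mechanism aim needs a result that one explanation predicts and its rival does not. A lower hypoxia rate is not such a result here. The CPAP arm receives a pressure intervention together with a particular interface and a protocol-set flow, while control oxygen is left to the treating providers.

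The protocol supplies the rival explanation itself. The Abstract calls oximetry a poor guide to ventilation in patients on supplemental oxygen. Section 3 speaks of oxygen preventing hypoxia, and describes the trial as a comparison of oxygen delivery. Section 9 describes success as a better way of delivering oxygen.

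Read alone, the last sentence of Aim 2 would let a pure oxygenation effect count as support for the airway-tone hypothesis. What is at stake is the mechanistic claim in the eventual report. The comparison of the nasal-mask package with usual care under Aim 1 is valid whichever route the effect takes.

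**Working it through.** **1. Is the primary calculation touched?** Inputs from section 7: hypoxia 13.5% against 1.8%, alpha 0.05 two-sided, power 0.9, 109 per arm.

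n = [1.960 × √(2p̄q̄) + 1.282 × √(p₁q₁ + p₂q₂)]² / (p₁ − p₂)², where p̄ = (0.135 + 0.018)/2 = 0.0765 and q̄ = 0.9235.

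- √(2 × 0.0765 × 0.9235) = 0.3759, times 1.960 = 0.737
- √(0.135 × 0.865 + 0.018 × 0.982) = 0.3667, times 1.282 = 0.470
- (0.737 + 0.470)² / 0.117² = 1.456 / 0.01369, about 106.4, so 107 per arm

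The stated 109 is within two patients of this. Full enumeration of the two-sided Fisher test at 109 per arm gives power 0.908. The concern disputes none of this, and rewording Aim 2 would change none of it.

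**2. Can the plan as written tell the explanations apart?** Set the possible results beside what each would mean:

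| Hypoxia, CPAP vs control | Obstruction, minute ventilation, transcutaneous CO2 | Reading |
|---|---|---|
| Lower | Better under CPAP | Supports airway-tone mechanism |
| Lower | No difference | Points towards oxygen delivery |
| No difference | Better under CPAP | Airway effect without fewer desaturations |
| No difference | No difference | No support |

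The first column is the primary outcome. The second consists of secondary outcomes in sections 4 and 7, with their direction stated in section 3. Every row can be seen from results that will be reported anyway, including the awkward second row.

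**3. How large is the oxygen component?** It cannot be computed. The protocol gives no control-arm device split, flow or start time, so neither the direction nor the size of any oxygen difference is known. An unstated start time is not evidence of a later one.

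**4. How sensitive are the separating comparisons?** This is illustrative and does not size the concern. With 109 per arm and two-sided 0.05, the detectable difference in a continuous outcome is (1.960 + 0.842) × √(2/109) = 0.38 SD at 80% power, and (1.960 + 1.282) × √(2/109) = 0.44 SD at 90%.

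For any obstructive episode under Fisher's test, no control rate is given. At assumed control rates from 10% to 90%, the fall detectable with 80% power runs from about 9 points (10% to 1.1%) to about 20 points (60% to 40.2%). These figures carry no multiplicity adjustment. They treat obstruction as any against none and use a simple two-group comparison, whereas section 3 also speaks of rate and degree and section 7 allows regression and mixed models. These limits are the same however Aim 2 is worded.

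**5. What would rewording add?** The natural remedy is to rest the mechanistic conclusion on the three between-arm comparisons, treat hypoxia as corroborating, and tabulate oxygen delivery and manoeuvres by arm. It adds no analysis to those already listed. It does not say whether one, two or all three measures must move. Flow changes and manoeuvres are already logged, and initial device, flow and start time plausibly fall under the routine clinical data that are collected.

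**The case for a change.** The strongest case for a change is that mechanism is the declared object of Aim 2, yet its only between-arm inference uses hypoxia. The first part of the hypothesis describes associations between ventilation, hypoxia and obstruction, and does not set a randomised criterion. Neither Aim 2 nor section 7 makes the conclusion depend on obstruction or ventilation. With unblinded providers, choosing the mechanistic evidence after seeing the data would be less credible than naming it beforehand, and naming it costs one sentence.

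Part of this stands. Hypoxia alone cannot discriminate, and Aim 2 lacks a cross-reference. Section 7 also gives only general methods, with no specific between-arm model or summary measure for obstruction, minute ventilation or transcutaneous CO2.

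The rest does not carry. The separating outcomes and their expected direction are already in the protocol, so naming them is not left until after the data. A sentence in Aim 2 would not supply the missing summary measures. Nor are those outcomes free of the same difficulty: unblinded manoeuvres can alter obstruction counts, and section 3 notes that oxygen may affect respiratory drive. Moving the emphasis to them would not by itself isolate airway tone.

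**Conclusion.** No change is needed. The concern correctly identifies a rival explanation, but the sentence it challenges says only that a result would fit a hypothesis, which is true. Read as a whole, the protocol does not rest mechanism on hypoxia alone, and a competent analyst would set the primary result beside the obstruction, minute ventilation and transcutaneous CO2 comparisons before discussing mechanism.

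The effect on the primary test, the 109 per arm and the planned enrolment of 240 is nil. The effect on the mechanistic reading cannot be quantified from the documents.

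This conclusion assumes that the listed secondary outcomes are compared between arms, as section 3 implies, and that the logged flow changes and manoeuvres are available when results are interpreted. A cross-reference in Aim 2 and a descriptive account of oxygen delivery by arm would help readers, but they are optional and would alter no result.

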Impedance based respiratory volume monitoring has been used to assess adequacy of ventilation and airway obstruction in patients undergoing endoscopic gastrointestinal procedures. In fact, such studies also suggest that EtCO2 often decreases as minute ventilation decreases. In this study, changes in minute ventilation from baseline, and episodes of upper airway obstruction will be assessed using the commercially available ExSpiron™ (Exspiron, Respiratory Motion Inc, Waltham MA). Previous studies using the ExSpiron™ have suggested that decreased minute ventilation during sedation for GE procedures is primarily due to decreased tidal volume rather than respiratory rate. Transcutaneous carbon dioxide has proven to closely approximate to arterial carbon dioxide (PaCO2), and in fact more closely reflects PaCO2 than end tidal carbon dioxide (EtCO2). Transcutaneous carbon dioxide (TcCO2) has been shown to closely correlate with PaCO2. After approximately 5 minutes of calibration time, it appears to track changes in PaCO2 with a lag time of 30 seconds to 2 minutes. In our experience using the TcCO2 monitor

for clinical application during jet ventilation, we have found the device to consistently track within 5 points of the PaCO2. (Sentec, Therwil, Switzerland).

Depth of anesthesia using processed electroencephalography has been described as a marker for depth of anesthesia during GETA and MAC with sedation. Depth of anesthesia using bispectral index (BIS) has been relatively well established and is known to correlate well with other measures of depth of anesthesia. We will use bispectral index (BIS) (Medtronic, Minneapolis, Minnesota) as a marker of state. In addition, all clinical data utilized in routine practice will be recorded, including drug dosing, method of drug administration, and length of stay in the recovery area.

Recently, alterations in the gut microbiome have been implicated in obesity, hypertension, obstructive sleep apnea induced hypertension, and airway smooth muscle tone that may relate to reactive airway disease. In general, lower short chain fatty acid levels are associated with pathology, and higher levels appear to be

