## 7. Study Statistics

### a. Primary outcome variable.

The primary outcome will be the rate of hypoxia below 90% for  $\geq 15$  seconds.

- ### b. Secondary outcome variables. Secondary outcomes will include change in respiratory parameters (tidal volume, respiratory rate, minute ventilation, obstructive events), hypoventilation by TcCO2, EtCO2, and depth of anesthesia by BIS, as well as demographic differences. Demographic information to the occurrence of hypoxic events will be analyzed with logistic regression.

Statistical plan including sample size justification and interim data analysis.

Power analysis is based on a previous German study in the literature, of patients undergoing upper and lower endoscopy with hypoxia rates of 13.5% with standard care and 1.8% with application of nasopharyngeal airway. Using these figures to perform a power analysis for the primary outcome of hypoxia below 90%, with alpha 0.05 and power of 0.9, approximately 109 subjects in each arm or a total of 218 subjects will be needed. In order to obtain 109 completed subjects in each arm and to allow for those participants with incomplete datasets (e.g. monitor failure), we will enroll 120 subjects in each arm and a total of 240 subjects.

Frequency data will be analyzed with Fisher's Exact Test, ordered categorical data will be analyzed with the rank sum test, and continuous data will be analyzed with regression or equivalent techniques. Therefore, our primary outcome as to the incidence of hypoxia in each arm of the study will be determined using Fisher's exact test. All time series data from multiple sources will be aligned using the associated time stamp with the aid of the program data manipulation capabilities in Mathematica 11. Longitudinal analysis will be performed using a mixed model approach, initially with random intercepts alone, with the addition of nonlinear terms and interaction as indicated by the resulting model. Throughout, findings will be considered significant for  $p < 0.05$  and  $p$  values will be determined using two-sided tests. Statistical analysis will be performed with the aid of Stata 13. An analysis will be performed after the first 20 subjects to ensure complete data collection and to run a batched analysis of SCFA to evaluate this aim. An interim data analysis will be done after ~120 subjects have been enrolled.

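### Ventilation outcomes are worded as changes, with no baseline adjustment named and no rule that baseline precedes the one-arm CPAP mask; compare arms on the on-sedation value adjusted for a pre-mask baseline

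*Combined protocol and SAP*

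**What the plan says.** Three places describe the ventilation outcomes. Section 3 (Background) states that "changes in minute ventilation from baseline, and episodes of upper airway obstruction will be assessed" using the impedance monitor. Section 4 (Study Procedures) lists the change in minute ventilation among the secondary outcomes. Section 7b states: "Secondary outcomes will include change in respiratory parameters", and names tidal volume, respiratory rate and minute ventilation. Only section 3 gives the reference point as baseline. No section says when baseline is read, over what window, or in what state.

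On timing, section 4 states: "Subjects randomized to nCPAP will have a nasal facemask (SuperNOVA) placed approximately 5 minutes prior to the procedural start". The control arm has no mask. All subjects wear the research monitors, but no time is given for applying them relative to the mask. For transcutaneous CO2, section 3 says that the device tracks arterial CO2 "After approximately 5 minutes of calibration time", with a lag of 30 seconds to 2 minutes. That outcome is described as the degree of hypoventilation, not as a change.

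On analysis, section 7 plans regression or a comparable technique for continuous data, and a mixed model starting from random intercepts for longitudinal data. Neither mentions a baseline term. Section 3 hypothesizes less hypoventilation in the CPAP arm, and section 7 applies a two-sided 0.05 level throughout, so a between-arm test of these outcomes is to be expected.

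**The concern.** There are two separate issues.

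The first is precision. Subtracting baseline gives it a coefficient of exactly 1. Unless baseline and sedated values are almost perfectly correlated, this adds noise that a fitted coefficient would not. The trial already records the baseline, so the better analysis needs no new data.

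The second is conditional. The mask is part of the randomized treatment. A baseline read after it is placed would be read on CPAP in one arm and off CPAP in the other. Any effect of the mask on awake breathing would then be subtracted from one arm only, which could hide a real difference or create a false one. A larger sample does not cure this. The text does not say that baseline will be read this way, but it does not rule it out.

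At stake is the between-arm statement about hypoventilation, which is secondary but is the mechanistic message of the trial.

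**Working it through.** **The plan's own figure.** Section 7 takes "hypoxia rates of 13.5% with standard care and 1.8% with application of nasopharyngeal airway" and concludes: "with alpha 0.05 and power of 0.9, approximately 109 subjects in each arm or a total of 218 subjects will be needed". The tests are two-sided ("values will be determined using two-sided tests"). The pooled normal formula is

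n = [1.960 × sqrt(2 × p̄ × (1 − p̄)) + 1.282 × sqrt(p1(1 − p1) + p2(1 − p2))]² / (p1 − p2)²

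With p1 = 0.135, p2 = 0.018 and p̄ = 0.0765 it gives 107 per arm, within 2 of the stated 109. Exact Fisher power at 109 per arm is 0.908. This calculation uses no baseline, so the point does not touch it. I use 109 per arm below as the number of completed subjects. The plan states: "we will enroll 120 subjects in each arm and a total of 240 subjects".

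**Inputs that the documents do not give.** These are the standard deviation of minute ventilation, its baseline-to-sedation correlation (rho), and any effect of the mask on awake ventilation (b). All are assumed and shown as ranges. The standard deviation is set to 1 and taken as equal at baseline and under sedation.

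**Precision.** Variance per subject is

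- difference score: 2(1 − rho)
- sedated value adjusted for baseline (ANCOVA): 1 − rho²
- ratio, ANCOVA to difference score: (1 − rho²) / [2(1 − rho)] = (1 + rho)/2

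| rho | difference score | ANCOVA | reduction | 109 per arm on a difference score is worth | power for an assumed 0.40 SD effect, difference score / ANCOVA |
|---|---|---|---|---|---|
| 0.3 | 1.40 | 0.91 | 35% | 71 | 0.70 / 0.87 |
| 0.5 | 1.00 | 0.75 | 25% | 82 | 0.84 / 0.93 |
| 0.7 | 0.60 | 0.51 | 15% | 93 | 0.97 / 0.99 |

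The fifth column is 109 × (1 + rho)/2. At rho = 0.9 the ratio is 0.95 and little is left to gain. Below rho = 0.5 the difference score is less precise even than the unadjusted sedated value, whose variance is 1.

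**Bias, only if baseline is read on CPAP.** Suppose that the mask shifts awake ventilation by b SD in the CPAP arm, and that the arms do not truly differ under sedation. The expected contrast is then

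- difference score: −b
- ANCOVA on the post-mask baseline: −rho × b
- ANCOVA on a pre-mask baseline: 0

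The standard error is sqrt(2V/109), with V the variance from the formulas above. At rho = 0.5 it is sqrt(2 × 1.00/109) = 0.135 for the difference score and sqrt(2 × 0.75/109) = 0.117 for ANCOVA. The false-positive rates at a nominal two-sided 0.05 are:

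| b (SD, assumed) | difference score | ANCOVA, post-mask baseline |
|---|---|---|
| 0.1 | 0.114 | 0.071 |
| 0.2 | 0.315 | 0.136 |
| 0.3 | 0.601 | 0.248 |

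Adjustment shrinks the bias but does not remove it. Only a pre-mask baseline does.

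**The case against.** The strongest reply is that the plan never prescribes a change-score test. The baseline wording comes from the Background, and the methods named in section 7 can both carry a baseline term. This stands: the defect is an omission. A regression of the change with baseline as covariate would even give the same arm effect as ANCOVA. But the outcome is worded as a change and no covariate is named, so two analysts could follow the text and differ.

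Second, a reader might infer that baseline will be read on CPAP, because the mask lead time and the transcutaneous CO2 settling time are both about 5 minutes. The documents do not support that. Section 4 describes the research monitors before the mask, and describes calibrating the CO2 sensor before applying it. The settling time also says nothing about when the impedance monitor reads minute ventilation. Narrative order is not a schedule, however, so the bias remains possible, with unknown sign and size.

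Third, a reader might extend the point to transcutaneous CO2 as a change score, or conclude that Aim 2 rests on this contrast. Neither follows. Transcutaneous CO2 is worded as a degree of hypoventilation. Aim 2 mainly relates ventilation to hypoxia, sedation depth and obstruction, and its between-arm element is the incidence of hypoxia.

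Fourth, with a pre-mask baseline both analyses are unbiased under randomization, and ANCOVA is then only a gain in efficiency for outcomes that were not powered. That is correct, but the gain is almost free.

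**Conclusion.** The point holds as an improvement to the analysis of secondary outcomes. Minute ventilation, tidal volume and respiratory rate are worded as changes, no baseline adjustment is named, and baseline is not required to precede a mask worn in one arm only. Adjusting the on-sedation value for baseline cuts variance by 35%, 25% and 15% relative to a difference score at rho of 0.3, 0.5 and 0.7. These figures assume equal standard deviations and apply to differences, not to percent of baseline. The correlations are not in the documents.

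The bias is a possibility, not a finding. It arises only if baseline is read on CPAP and the mask alters awake ventilation, and the false-positive rates above show what would follow under assumed shifts. The primary comparison and the sample size stand as they are.

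**What to change.** Make two changes to the statistical section, with a matching line in Study Procedures.

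1. For the arm comparison of minute ventilation, tidal volume and respiratory rate, model the on-sedation value with baseline as a covariate: ANCOVA for a per-subject summary, or a baseline term in the mixed model for the time series. Change from baseline can still be reported descriptively.
2. Define baseline as a summary over one awake, pre-sedation window of stated length, before the mask is placed and read the same way in both arms. State how a missing baseline will be handled.

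For transcutaneous CO2, the value from the same window, once the sensor has settled, is simply a useful covariate.

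The window must fit around clinical care: the change concerns when research readings are taken and leaves oxygen management and mask placement as they are. The cost is a few lines of text and applying the research monitors a few minutes before the mask, with no added patients or equipment. The data-completeness check already planned after the first 20 subjects can confirm that the window is being captured.
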